1.1 Study Objectives

1.1.1 Objectives

Objective 1: To develop and refine PICT, an intervention to train family caregivers of PWD how to administer an observational pain assessment tool and communicate the results to health care providers.

Objective 2: To evaluate the feasibility and acceptability of the finalized version of PICT among family caregivers of PWD and health care providers

Objective 3: To test the preliminary efficacy of PICT on 1) caregiver ability to identify pain symptoms; and 2) caregiver efficacy in communicating with health care providers

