1.1.2 Hypotheses / Research Questions

Hypothesis 1: As this study objective involves intervention development only, no hypotheses are given.

Hypothesis 2a (feasibility): 70% or more of participants will meet the benchmark for feasibility, defined by participant retention and adherence to the intervention.

Hypothesis 2b (acceptability): 70% or more of participants will meet the benchmark for acceptability, defined by participant ratings on questionnaires related to “helpfulness,” “future use,” and “overall comprehension” of the intervention content.

Hypothesis 3: PICT will be more effective than an attention control for improving caregivers’ ability to identify pain in PWD and to initiate pain related-communication with health care providers.

2. Background and Significance

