4.4 Strategies for Recruitment and Retention

Overview of Caregiver Recruitment Procedures

Co-investigators will meet with health care providers who see patients at the Center on Aging, the Alzheimer's Disease and Memory Disorders Program, and Weill Cornell Internal Medical Associates to make them aware of the study protocol, including the plan to send recruitment letters (postal mail or email) to their patients' caregivers. During the meetings, the co-investigators will ask each provider to review his or her patient list and identify individuals who have both pain and dementia, as well as a family caregiver. When meeting with these healthcare providers, co-investigators will verify that the caregiver lives with the patient and/or obtain the caregiver contact information from the providers. Recruitment letters will then be sent by mail or email (when available) to the caregivers of the identified patients. Patients themselves will not be contacted, and every effort will be made to contact the caregiver directly. When possible, letters will be sent to the emergency contact (i.e., caregiver) if their telephone matches that of the patient, or by email. The recruitment letter will describe the study and advise caregivers that they may decline participation by emailing or placing a telephone call to the study team. Approximately 2 weeks after the initial letter (postal mail or email) is sent, caregivers who have not opted out will be telephoned or emailed by the trained co-investigator to confirm their interest.

For caregivers that care for a patient at recruitment sites, patients' medical records will first be reviewed by a trained co-investigator who will confirm whether or not they meet eligibility criteria (dementia and pain diagnosis). Recruitment site caregivers will be approached in the waiting room prior to their doctor's visit. The co-investigator will perform the consenting process either in the waiting room or a private office, if available.

Other caregivers will be recruited via caregiving resources and groups in the community including the WCM/NYP Geriatrics caregiver support groups, local community centers, senior service agencies, etc. Interested individuals will provide their name and contact details on a sign-up sheet.

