7.2.5 Record Retention

Essential documents are those documents that individually and collectively permit evaluation of the study and quality of the data produced. After completion of the study, all documents and data relating to the study will be kept in an orderly manner by the Investigator in a secure studyfile. Essential documents should be retained for 2 years after the final marketing approval in an ICH region or for at least 2 years since the discontinuation of clinical development of the IP. In addition, all subject medical records and other source documentation will be kept for the maximum time permitted by the hospital, institution, or medical practice.

8. Statistical Considerations

Interviews: Interview transcripts will be analyzed according to the constant comparative method, in which new concepts are compared to existing codes (labels that catalog key concepts), existing codes are refined, and a coding structure is developed in stages. This process will continue until theoretical saturation is reached - the point at which no new information is generated from additional interviews.

Pilot testing: statistical considerations. Feasibility will be examined in terms of rates of recruitment and number of sessions completed by participants in the intervention condition. Preliminary analyses to compare the intervention vs. control group on PWD and caregiver sociodemographic characteristics will be carried out in linear models (for continuous variables) and logistic-linear models (for categorical variables). The effectiveness of the intervention will be evaluated in a statistical model that includes treatment (control vs. intervention) and time of assessment (baseline vs. 4 weeks post intervention) as fixed classification factors; the interaction of treatment and time; covariates such as age and gender; and family caregivers (30 per treatment group) as levels of a random classification factor. The primary dependent variable (caregiver contacts primary care practice) is dichotomous, and analysis is by a logistic-linear mixed model with binomial error. Self-efficacy will be included in the model as a fixed classification factor (categorized in 2 levels) as will its interaction with treatment and time. Interactions with other key sociodemographic and clinical variables will also be examined.

9. Adverse Event Reporting Requirements

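### The primary outcome, contact with a primary care practice, does not measure what Hypothesis 3 and Objective 3 are about: pain communication with health care providers of any kind

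*Combined protocol and SAP*

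**What the plan says.** Section 8 (Statistical Considerations, pilot testing) names one primary variable: "The primary dependent variable (caregiver contacts primary care practice) is dichotomous". It adds that "analysis is by a logistic-linear mixed model with binomial error". It gives no coding rule, data source, look-back window or definition of a primary care practice, and it does not say that the contact must concern pain.

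The aims are worded more broadly. Objective 3 (Section 1.1.1) includes "caregiver efficacy in communicating with health care providers". Hypothesis 3 (Section 1.1.2) predicts that PICT will improve caregivers' ability "to initiate pain related-communication with health care providers". Neither is limited to primary care.

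Section 4.4 names the Center on Aging together with "the Alzheimer's Disease and Memory Disorders Program, and Weill Cornell Internal Medical Associates" as clinical sources. It then says: "Other caregivers will be recruited via caregiving resources and groups in the community". Flyers, online platforms, a participant registry and snowballing are added. The eligibility criteria (Sections 4.2 and 4.3) do not require the person with dementia to have a primary care practice, or that practice to manage the pain.

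**The concern.** The outcome and the hypothesis differ in two respects, and the two differences produce opposite errors.

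- **Provider.** The hypothesis covers any health care provider; the variable covers one type. A caregiver who raises pain with a memory, palliative or pain clinician and never contacts primary care shows the predicted behaviour but would not be counted.
- **Content.** The hypothesis is about pain; the variable is about contact. A call to primary care on an unrelated matter would be counted.

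Recruitment reaches well beyond primary care, so the first case is plausible in this sample. What is at stake is the preliminary efficacy estimate, one of the pilot's three objectives. A result on this variable, positive or null, would not directly answer Hypothesis 3. With the term undefined, two coders could also classify the same contact differently.

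**Working it through.** **Text comparison.** Outside the reference list, primary care appears as a term only in the Section 8 outcome sentence. The caregiver workbook and the post-test content described in Section 3.1 refer to health care providers without restriction. No section widens the outcome or explains the narrowing.

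**Is there a figure to reproduce?** No. The documents give no contact rates, effect size, significance level, power or dropout. What follows only illustrates the mechanism.

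**Inputs from the documents.** 50 caregivers per arm (Section 3.1) and 30 per arm (Section 8). The two conflict, which is a separate matter, so both are shown.

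**Assumed inputs.** True pain communication with any provider of 30% (control) and 60% (PICT); two-sided 5% test; a share s of communicating caregivers, equal in both arms, who contact only clinicians outside primary care. The word only matters: a caregiver who contacts both a specialist and primary care is still a yes.

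**Formulas.** Observed rates are a = 0.30(1 − s) and b = 0.60(1 − s), so the difference is 0.30(1 − s). With m = (a + b)/2 and d = b − a,

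power = Φ{ [d√n − 1.96√(2m(1 − m))] / √(a(1 − a) + b(1 − b)) }.

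**Worked case, s = 0, n = 50.** d√n = 0.30 × 7.071 = 2.121. m = 0.45, so 1.96√0.495 = 1.379. The denominator is √(0.21 + 0.24) = 0.671. (2.121 − 1.379)/0.671 = 1.107, giving 86.6%.

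**Worked case, s = 30%, n = 50.** Rates are 21% and 42%. d√n = 0.21 × 7.071 = 1.485. m = 0.315, so 1.96√0.43155 = 1.288. The denominator is √(0.1659 + 0.2436) = 0.640. (1.485 − 1.288)/0.640 = 0.308, giving 62.1%.

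| s | Observed rates | Difference (points) | Power, 50 per arm | Power, 30 per arm |
|---|---|---|---|---|
| 0 | 30% vs 60% | 30 | 86.6% | 65.3% |
| 10% | 27% vs 54% | 27 | 79.4% | 57.0% |
| 20% | 24% vs 48% | 24 | 71.1% | 49.0% |
| 30% | 21% vs 42% | 21 | 62.1% | 41.5% |

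**The opposite error.** The table ignores primary care contacts that are not about pain. Suppose a fraction r of the caregivers otherwise recorded as no make such a contact, with the same r in both arms. Each observed rate becomes a + r(1 − a) or b + r(1 − b), and the difference becomes (1 − r)(b − a). Both rates rise, but the difference shrinks further. Under that assumption the two errors do not cancel in the risk difference. If r differs between arms, or is higher among caregivers who speak to specialists, this no longer holds. The documents give nothing from which to estimate s or r.

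**The case against.** Several points on the other side are sound. Section 8 gives only a short label. A reader might infer that the plan scores pain communication with other clinicians as failure. No such rule is written; that is the literal reading of a variable name, and a coding manual could treat the Center on Aging or the memory program as primary care.

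A reader might also infer that caregivers recruited at the memory program, or online, will bypass primary care, or that PICT steers them to specialists. The documents support neither. Recruitment source does not show where a patient's pain is managed, and two other clinical sources are listed beside the memory program.

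The power figures come from a simple two-proportion test. Section 8 specifies a logistic mixed model with a treatment-by-time interaction, and no planned power exists against which to measure a loss.

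Finally, a narrow behavioural endpoint can be a legitimate choice in a pilot, and the post-test also asks about comfort and confidence in communicating with providers.

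These points limit how large the problem can be said to be. They do not remove the mismatch: if the restriction to primary care is deliberate, Hypothesis 3 should say so and give a reason, and it does not. The missing pain requirement remains on any definition of primary care.

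**Conclusion.** The concern holds as a mismatch between outcome and hypothesis. The variable as named leaves out part of the behaviour in Hypothesis 3 and admits behaviour outside it. This is more than missing detail, because defining primary care practice more fully would still leave the pain requirement absent and other clinicians excluded.

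The effect on the trial cannot be sized from the documents. The loss of 3 to 9 points in the difference, and the matching fall in power, depend on the assumed 30% and 60% rates, an equal share of 10% to 30% in both arms, no contacts unrelated to pain, and a simple test. They show that a modest share could matter at these sample sizes; they do not forecast this trial's power. The change should be made before the outcome is analysed.

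**What to change.** In Section 8, redefine the primary dependent variable as caregiver contact about pain with any health care provider treating the person with dementia. Ask it in identical words in both arms at pre-test and post-test. State the data source and look-back window. Record provider type (for example primary care, memory or neurology, palliative or pain, other) and report primary care contact as a prespecified breakdown, so that no information is lost.

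If primary care is the intended target, the alternative is to restrict Hypothesis 3 to it, justify that, define the term and add the pain requirement.

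The cost is a revised sentence or two in Section 8 and possibly one added or amended questionnaire item; the questionnaires are not reproduced, so the existing items are unknown. One small downside is that the wider definition may raise the control-arm rate.

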Participants in both conditions will be asked to complete an identical pre-test questionnaire. The questionnaire will be sent to via email or postal mail, and/or will be scheduled to be completed over the phone. We will ask about the participant's background, caregiving role, and comfort speaking with health care providers. It will take approximately 15-20 minutes to complete.

Intervention condition. Participants in the intervention condition will be contacted by a member of the study team to start the PICT workbook. The PICT workbook consists of four sessions and will be completed over the telephone with a study team member. Sessions are conducted once a week and last approximately 30-60 minutes each. Participants will also be asked to read sections of the PICT workbook and complete exercises between sessions. The reading and exercises will take 10-15 minutes to complete. After the final session of the intervention, a study team member will contact the participant by telephone to complete another set of questionnaires (at 12 weeks after the pre-test questionnaire). The questionnaire will be sent to via email, postal mail, or will be scheduled to be completed over the phone. The post-test questionnaires will take approximately 20 minutes to complete and will ask about the participant's comfort and confidence in communicating with health care providers, behaviors he or she observes in the recipient, and views of the PICT workbook. Participants will also be asked to participate in a 20-30 minute telephone interview to elaborate their responses to the questionnaire. Participants must agree to be audiotaped to participate in the study.

Control condition. Caregivers in the control condition will receive an informational pamphlet about pain in dementia and a link to the Alzheimer's Association website. Twelve weeks after the participant completes the pre-test questionnaire, she or he will be contacted by a member of the study team to complete the post-test questionnaire. The questionnaires will be sent via email, postal mail, or will be scheduled to be completed over the phone and will take approximately 20 minutes to complete.

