3.2 Interviews, Focus Groups, Surveys, and/or Observations

A. Administration

- *Timing and Frequency*
 - Interview and field-testing phases: Caregiver and healthcare professional subjects will complete a one-time 20-30 minute interview accompanied by a brief questionnaire. Interviews will be conducted by a research nurse or trained co-investigators.
 - Pilot testing phase: PICT will consist of 4 weekly 30-60-minute sessions delivered by a study team member. In between sessions, participants will have 10-15 minutes of reading and exercises to complete.
- *Location*

Interview and field testing phases will take place in-person in private offices at WCMC/NYP or over the telephone. The participant, in special circumstances (e.g. scheduling issues) may opt to have the interview take place in a private location convenient to them.

Pilot testing will take place over the telephone.
- *Procedures For Audio And Visual Recording*

All interviews will be recorded and transcribed by a certified, secure, and WCM-approved transcription agency.
- *Person Identifiers*

Co-investigators may review EPIC to identify potential participants who meet eligibility. Contact information and appointment information will also be collected for either in-person or letter (postal and email) recruitment. Only data from potential participants will be stored on secure servers. These data will be deleted upon completion of the study or immediately if a patient chooses not to participate in the study.

B. Study Instruments

Interview Phase 1

- Caregiver subjects
 - Screening questions
 - Caregiving questions
 - Brief cognitive screener (BOMC)
 - Brief Questionnaire – Caregiver
 - Demographics
 - Caregiving Questions
 - Patient Health Characteristics
 - Interview Guide – Caregiver
 - Field test questions - Caregiver
- Healthcare Professional subjects
 - Brief Questionnaire – Provider
 - Demographics
 - Medical practice questions
 - Interview Guide – Provider
 - Field test question – Provider

Pilot Test Phase

- Caregiver subjects in PICT (intervention) group
 - Pre-test Questions for All Caregiver Participants
 - Post-test Questions for Caregivers in PICT Group
 - Exit Interview Questions
- Caregiver subjects in control group
 - Pre-test Questions for All Caregiver Participants
 - Post-test Questions for Caregivers in Control Group

4. Study Design

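### Objective 3 makes caregiver communication efficacy an outcome, but Section 8 gives no between-arm analysis of it and uses self-efficacy only as a two-level predictor

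*Combined protocol and SAP*

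**What the plan says.** Section 1.1.1, Objective 3, lists two outcomes for preliminary efficacy: ability to identify pain symptoms, and "2) caregiver efficacy in communicating with health care providers". Hypothesis 3 (Section 1.1.2) words the second differently, as initiating communication about pain with providers.

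Section 8, under pilot testing, describes one effectiveness model: treatment, time, their interaction, covariates and a random caregiver effect. It then states: "The primary dependent variable (caregiver contacts primary care practice) is dichotomous", to be analysed with binomial error. The next sentence reads: "Self-efficacy will be included in the model as a fixed classification factor (categorized in 2 levels) as will its interaction with treatment and time". The only other between-arm comparison in Section 8 is of sociodemographic characteristics.

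On measurement, Section 3.1 says the pre-test is identical in both arms and covers "caregiving role, and comfort speaking with health care providers". Under the intervention condition, the post-test covers "comfort and confidence in communicating with health care providers". Under the control condition the text says only that "she or he will be contacted by a member of the study team to complete the post-test questionnaire", without describing its content. Section 3.2 B lists two separate instruments, "Post-test Questions for Caregivers in PICT Group" and "Post-test Questions for Caregivers in Control Group".

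**The concern.** An outcome named in an objective should have an analysis that compares the arms on it. Here the construct appears only as an explanatory factor. The interaction of self-efficacy with treatment and time asks whether PICT's effect on contact differs between caregivers with low and high self-efficacy. It does not ask whether PICT changes communication efficacy.

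Three things are at stake:

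- **The missing estimate.** The pilot would report on one of Objective 3's two outcomes with neither a difference between arms nor a measure of its uncertainty.
- **Measurement in controls.** If the control post-test omits the scale, the gap is permanent, so the check has to come before post-tests are collected.
- **Timing of the factor (lesser).** Section 8 does not say when self-efficacy is measured. A pre-test value is a legitimate moderator. A post-test or time-varying value would condition the effect on contact on something PICT is meant to change.

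**Working it through.** The plan gives no figure for this outcome, so there is none to reproduce. The check is textual, followed by the precision of the missing estimate and an illustration of the timing point.

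**1. Outcomes against analyses**

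| Item | Place | Role in Section 8 |
|---|---|---|
| Communication efficacy | Objective 3 | Not a dependent variable |
| Initiating communication about pain | Hypothesis 3 | Partly covered by contact with the practice |
| Self-efficacy | Section 8 only | Two-level predictor, with interactions |

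Section 8 does not tie self-efficacy to communication. Treating it as the Objective 3 construct is an inference. If it is something else, communication efficacy is absent from Section 8 altogether. The gap exists on either reading.

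**2. Precision of the between-arm difference**

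Inputs from the documents: 50 per arm (Section 3.1) and 30 per arm (Section 8). These conflict, so both are shown. Assumed: pre–post correlation r of 0.3, 0.5 or 0.7, and 70% post-test completion, equal in both arms, as an alternative to full retention. The documents give neither.

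Half-width of the 95% confidence interval, in SD of the post-test score:

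- unadjusted: t(0.975, 2n−2) × √(2/n)
- adjusted for pre-test: t(0.975, 2n−3) × √[(2/n)(1−r²)]

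At n = 50, unadjusted: 1.984 × √(2/50) = 1.984 × 0.200 = 0.40. Adjusted at r = 0.5: 1.985 × √(0.04 × 0.75) = 0.34.

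At 70% completion, 0.7 × 50 = 35 and 0.7 × 30 = 21.

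| n per arm | Unadjusted | r = 0.3 | r = 0.5 | r = 0.7 |
|---|---|---|---|---|
| 50 (full) | 0.40 | 0.38 | 0.34 | 0.28 |
| 30 (full) | 0.52 | 0.49 | 0.45 | 0.37 |
| 35 (70% of 50) | 0.48 | 0.46 | 0.41 | 0.34 |
| 21 (70% of 30) | 0.62 | 0.60 | 0.54 | 0.45 |

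If controls do not receive the scale, there is no between-arm estimate at any n.

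**3. Timing of the self-efficacy factor (illustration; every input assumed)**

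A random-intercept logistic model for contact at two assessments was fitted to 10 simulated data sets of 40,000 caregivers per scenario. Fixed inputs were intercept −0.5, random-intercept SD 1.0, pre–post self-efficacy correlation 0.5, a median cut, sum-to-zero coding with all interactions, no unmeasured common cause and no other covariates. Entries are large-sample treatment-by-time odds ratios.

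| PICT effect on self-efficacy; log-odds of contact per SD; direct effect (log-odds) | Without self-efficacy | Value at each assessment | Pre-test value |
|---|---|---|---|
| 0.8 SD; 1.0; none | 2.10 | 1.33 | 2.07 |
| 0.5 SD; 0.5; 0.4 | 1.89 | 1.63 | 1.89 |
| 0.2 SD; 0.3; 0.4 | 1.57 | 1.52 | 1.57 |

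The Monte Carlo standard error of each log odds ratio is 0.011 to 0.014. For the difference from the model without self-efficacy it is at most 0.0053 (value at each assessment) or 0.001 (pre-test value). The pre-test reading leaves the effect essentially unchanged. The time-varying reading pulls it towards 1, most where the effect runs wholly through self-efficacy.

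**The case against.** The strongest reply has four parts.

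- **The model may be a general framework.** Section 8 introduces it before naming a dependent variable, and calling contact primary implies that others exist. This is a fair reading of the sentence order. But no other dependent variable is named, the only error structure given is binomial, and self-efficacy is explicitly a predictor. The framework reading still supplies no stated analysis of communication efficacy.
- **Contact may be the intended measure.** Objective 3 and Hypothesis 3 list parallel pairs, so efficacy in communicating could have been made operational as initiating communication. The documents do not rule this out, and contact does partly serve Hypothesis 3. However, contact is a behaviour, while the questionnaires separately collect self-rated comfort and confidence, for which no analysis is given.
- **Nothing shows that controls lack the scale.** True. Separate forms could be explained by the workbook questions, which apply only to the PICT arm, and both forms take about 20 minutes. The point is therefore a check to make, not a defect shown.
- **The timing point is small.** Also fair. The following sentence, on interactions with other sociodemographic and clinical variables, leans towards a pre-test value, and the largest distortion above needs an effect wholly mediated by self-efficacy.

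It is also true that a treatment-by-time mixed model for the score, with a suitable error structure, would give a between-arm estimate and keep caregivers who have only a pre-test. The need is for a stated analysis, and more than one would serve.

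**Conclusion.** The concern holds and should be fixed. Section 8 as written yields no between-arm estimate of communication efficacy. That conclusion rests on the text alone and does not depend on whether Section 8's self-efficacy is the same construct.

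With both arms measured, the unadjusted half-width runs from 0.40 SD (50 per arm, full retention) to 0.62 SD (21 per arm). Pre-test adjustment at r = 0.7 reduces these to 0.28 and 0.45 SD. The figures assume a roughly continuous score, and the adjusted ones assume the same scale at pre-test.

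Whether controls receive the scale at post-test is unknown from the documents. The timing point matters only if a value measured after randomisation is used, and its illustrated size depends entirely on assumed inputs. Section 8 likewise gives no model for pain identification, Objective 3's other outcome; that is outside this point.

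**What to change.** 1. Confirm that the same communication-efficacy scale is in both arms' post-test questionnaires, and name it. Also compare pre-test with post-test, since Section 3.1 mentions only comfort at pre-test but comfort and confidence at post-test.
2. Add to Section 8 a linear model of the uncategorised post-test score on assigned arm, adjusted for the pre-test score if the scale is the same. Report the mean difference with its 95% confidence interval. Analyse caregivers with a post-test score in their assigned arm, and give the number of missing post-tests by arm.
3. Report the treatment-by-time effect on contact from the model without self-efficacy. Restrict any self-efficacy factor or interaction to the pre-test value, in a separate exploratory moderation model.

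The cost is some wording in Section 8, a questionnaire check and slightly more analysis, and moderation becomes exploratory. If only the pre-test scale differs, the model is fitted unadjusted, at the wider half-widths. If the control post-test lacks the scale, it has to be added by amendment, and controls who have already completed post-test cannot contribute.

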encourage caregivers to ask questions (e.g., increasing visit time) and ways to address those concerns (e.g. instructing caregivers to ask only questions that are of particular concern). The interviews will also address formatting considerations of the caregiver workbook and provider manual (e.g. font size, language that is easy to understand, space for notes). Caregivers will also be asked to fill out a brief questionnaire that will be sent to participants along with the PAINAD tool by email or postal mail, or given to the participant prior to their interview. The questionnaire will include demographics, caregiving role, and patient health questions. Participants will be provided a self-addressed stamped envelope to mail this survey back; or they can use the WCMC secure file transfer to email back the questionnaire.

Field testing. Once initial versions of the PICT manual and workbook are developed, they will be iteratively field-tested and vetted by family caregivers (n=25 per iteration) and health care providers (n=20 per iteration). Participants will be recruited at WCM/NYP locations including the Center on Aging and Weill Cornell Medical Associates. After reviewing the PICT workbook, caregivers will complete a brief questionnaire about the content, format, and perceived utility of PICT, as well as ways to enhance its cultural relevance. They will also complete a brief (15-20 minute) semi-structured interview to clarify their perspectives. Health care providers will answer a similar set of questions. Results from this first field-test will inform the modified version of PICT and will address key issues, such as the feasibility of using research nurses (and other practice staff) to administer the intervention, anticipation of participant burden for caregivers, and adequacy of PICT format and instructions. Study procedures will be repeated (including IRB approval) with a new sample of caregivers (n=25) and providers (n=20). Results from the second field-test will be used to create the finalized intervention of PICT. Prior research indicates that a feasible intervention should be generated after two iterations.

Pilot testing. Family caregivers will be randomly assigned to PICT (n=50) or a control (usual care) condition (n=50).

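### The only effectiveness model includes a self-efficacy interaction, and no contrast is named for the overall PICT comparison in Hypothesis 3

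*Combined protocol and SAP*

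**What the plan says.** Hypothesis 3 (Section 1.1.2) is an overall comparison: "PICT will be more effective than an attention control". It names no self-efficacy subgroup.

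Section 8, under pilot testing, gives one model for it: "The effectiveness of the intervention will be evaluated in a statistical model that includes treatment (control vs. intervention) and time of assessment", followed by "the interaction of treatment and time; covariates such as age and gender" and a random effect for caregiver. The outcome and link are stated: "The primary dependent variable (caregiver contacts primary care practice) is dichotomous, and analysis is by a logistic-linear mixed model with binomial error". The next sentence adds to that same model: "Self-efficacy will be included in the model as a fixed classification factor (categorized in 2 levels) as will its interaction with treatment and time". Section 8 then says: "Interactions with other key sociodemographic and clinical variables will also be examined".

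Section 8 gives no version of the model without the self-efficacy terms. It also does not state:
- the term or contrast that tests Hypothesis 3;
- the coding of the factors, or any averaging over self-efficacy;
- the self-efficacy cut-point, or whether the value is taken before or after the intervention.

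Section 3.1 plans 50 caregivers per arm; Section 8 refers to 30 per arm.

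**The concern.** With treatment and time both in the model, the PICT effect on change in the outcome is the treatment-by-time term. Adding self-efficacy by treatment by time changes what that term estimates, and the meaning then depends on how the factors are coded. Two analysts following Section 8 faithfully could report different effects, with different precision, as the answer to Hypothesis 3, and the choice could be made after the data are seen.

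The timing of the self-efficacy measure adds to this. Caregiver efficacy in communicating with providers is itself an Objective 3 outcome (Section 1.1.1), and Section 3.1 has confidence in such communication asked at post-test. If the factor came from a post-test value, the model would condition on something PICT is meant to change.

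**Working it through.** The documents give no power calculation, event rate, effect size or alpha, so there is no stated figure to reproduce. The check compares the precision and target of treatment-by-time with and without the self-efficacy terms.

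**Inputs.** From the documents: two self-efficacy levels, two arms, two times, a logistic mixed model, and 50 (Section 3.1) or 30 (Section 8) per arm. Assumed: the share s of caregivers in one level, the same in both arms; similar information per caregiver in both levels; two-sided 5% tests.

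**1. Variance under the three-way reading.** Let V be the variance of treatment-by-time from all caregivers.
- Reference coding, effect at the level with share s: V/s.
- Equal-weight average: (1/4)(V/s + V/(1−s)) = V/(4s(1−s)).

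For a test that would have 80% power without the extra terms, power becomes Φ(2.802/√k − 1.960), where k is the variance factor.

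| Coding | Split | k | Power from an 80% base |
|---|---|---|---|
| Reference | 50/50 | 1/0.5 = 2.0 | 51% |
| Reference, larger level | 70/30 | 1/0.7 = 1.43 | 65% |
| Reference, smaller level | 70/30 | 1/0.3 = 3.33 | 34% |
| Equal weight | 50/50 | 1/(4×0.25) = 1.00 | 80% |
| Equal weight | 70/30 | 1/(4×0.21) = 1.19 | 73% |

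**2. Target.** Suppose the odds ratio is 2 in the larger level and 8 in the smaller, at 70/30. Averaging on the log-odds scale:
- equal weight: exp(0.5 ln 2 + 0.5 ln 8) = 4.0;
- sample weight: exp(0.7 ln 2 + 0.3 ln 8) = 3.03.

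At 50/50 both are 4.0. If the odds ratio is the same in both levels, all targets agree and only precision is at stake.

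**3. Simulation.** Two sets, 400 trials per setting, 50 per arm, random-intercept SD 1, no true moderation. Monte Carlo error is about 2.5 percentage points, from √(0.48×0.52/400).
- Mixed model by quadrature, contact 30% at baseline and 30% vs 60% at follow-up: power 58% without self-efficacy terms. With the three-way term it is 35% (reference, 50/50), 46% (reference, 70/30) and 47% (equal weight, 70/30), with no loss for equal weight at 50/50.
- Logistic fit with cluster-robust errors, intercept logit −1.4, odds ratio 4, 50/50 split: 48% without the terms, 26% reference, 48% equal weight, and 47% with only two two-way terms.

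**4. Two-way reading.** With self-efficacy by treatment and self-efficacy by time only, treatment-by-time is one common effect and loses almost nothing (47% against 48%). Whether the PICT effect on change differs by self-efficacy is the three-way term, which this model omits.

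**5. Cell sizes.** The smaller level holds 25 or 15 caregivers per arm and time at 50 per arm (50/50 or 70/30), and 15 or 9 at 30 per arm. In the second set of simulations (odds ratios equal or differing by level), the share of trials with at least one of the eight cells empty, all contacts or all non-contacts was:

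| Per arm | 50/50 | 70/30 |
|---|---|---|
| 50 | 1–2% | 8–9% |
| 30 | 11–14% | 29–32% |

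Under lower assumed contact rates (15% at baseline, 20% vs 50% at follow-up) and 70/30, the quadrature fit gave a coefficient above 8 in absolute value in 24% of trials at 50 per arm and 58% at 30 per arm. That is a different criterion and a harsher scenario.

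**The case against.** The best defence is that Section 8 is written in analysis-of-variance terms, with fixed and random classification factors. Under the tests that usually go with that wording, treatment-by-time is averaged over the self-efficacy levels. With a median split this average carries the sample's own weights and costs essentially nothing. The sentence may also mean two two-way terms, in which case treatment-by-time is untouched. And this is a pilot of preliminary efficacy with no stated power or decision rule.

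Much of that stands. A reader might infer three stronger things that the documents do not support:
- **That the planned test is a subgroup effect with roughly half the information.** That needs both the three-way form and reference coding, and Section 8 states neither.
- **That no reading can give both the overall effect and moderation.** A three-way model with a stated contrast averaged over self-efficacy gives both. Section 8 omits that contrast; it does not rule it out.
- **That the model is inherently too sparse to fit.** No contact rates or cut-point are given, and the risk ranges from about 1% of simulated trials to more than half, according to what is assumed.

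The further interactions are also weaker evidence: they are to be examined, not explicitly placed in this model.

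What the defence does not supply is the missing statement. The median split, the equal weighting and the two-way form are each possible, but none is written down.

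**Conclusion.** The point holds in a limited form. Section 8 puts self-efficacy and its interaction into the only effectiveness model and names no contrast for the overall comparison in Hypothesis 3. On the more natural three-way reading, the cost runs from nothing (equal weight, 50/50) through variance x1.19 (equal weight, 70/30) to x1.43, x2.0 or x3.33 (reference coding). The target shifts only when the split is uneven and effects differ by level. On the two-way reading the effectiveness test is sound, but moderation goes untested.

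Near-empty cells are a conditional risk (uneven split, low contact rates, or 30 rather than 50 per arm), not an established property of the plan. All splits, rates and odds ratios above are assumptions. Severity and confidence are moderate, and the change is a cheap improvement.

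**What to change.** In Section 8:
- State that the effectiveness result is the treatment-by-time contrast, with its 95% CI, from the model with treatment, time, their interaction, the named covariates and the caregiver random effect only.
- Fit self-efficacy by treatment by time in a separate exploratory model, and state that the three-way term is the moderation question.
- Define self-efficacy from a pre-test value and state its cut-point. Section 3.1 describes comfort in speaking with providers at pre-test but mentions confidence only at post-test, so confirm that the pre-test questionnaire contains the intended measure.
- Report the three-way term and any other interactions one at a time, as estimates with 95% CIs and no effectiveness claim.
- Reconcile the 50 per arm in Section 3.1 with the 30 per arm in Section 8.

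Keeping one model and pre-specifying an overall contrast with stated weights would also define the test, but the separate model is simpler and less exposed to thin cells. The cost is some wording, one extra model run, and moderation becoming explicitly exploratory. No new participants are needed.
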